## 2.3. Study Design

[figure not shown]
### Overview of Study Design and Key Features

#### Part A:

[figure not shown]

Interim decisions based on PK and safety data. Periods 4, 5 and 6 are flexible and the dosing regimen will be dependent on the outcome of the preceding periods.

#### Part B:

#### Part C:

Interim decisions based on PK and safety data. Periods 3 to 6 are flexible and the dosing regimen will be dependent on the outcome of the preceding periods.

Design Features	
 
An open label, single centre, three part, single and repeat dose study in healthy male and female participants to assess (matrix monolithic) MR and minitab MR formulations of GSK2982772 in a capsule and impact of food on absorption.
 
Part A – 6 period, sequential, 6-way fixed sequence design, with up to 4 MR minitab formulations evaluated after single dose of GSK2982772 120mg in the fasted state.
 
Part B – open-label, repeat dose to evaluate selected minitab MR formulation
 

------------------------	---

Overview of Study Design and Key Features	
	
(from Part A) following a 3 day repeat dosing of GSK2982772 at target daily doses of 30, 60 and 240mg (120mg, 240mg, 300mg actual daily doses).
 
 
Part C – 6 period, sequential, 6-way fixed sequence design, with MR (matrix monolithic) formulations evaluated after single dose of GSK2982772 240mg in the fasted state.
 

Dosing	
Part A:
 
 
Single dose of GSK2982772 120mg will be evaluated. Periods 1, 2 and 3 will evaluate a slow minitab MR release duration, a fast minitab MR release formulation and IR tablet respectively. Periods 4, 5 and 6 will be flexible and depend on outcomes from Periods 1 to 3 and may be used to optimise the MR release durations and/or to evaluate the food effect.
 
 
Part B:
 
 
Target total daily doses of GSK2982772 30, 60 and 120mg QD or BID (depending on Part A findings) will be evaluated for 3 days. This corresponds to actual daily doses of 120, 240, and 300mg, respectively. Administration of the minitab MR formulation will either be in fasted state or with a standard meal (depending on Part A findings)
 
 
Part C:
 
 
Single dose of GSK2982772 240mg will be evaluated. Periods 1 and 2 will evaluate a (matrix monolithic) MR formulation and an IR tablet, respectively. Periods 3 through 6 will be flexible and the dosing regimen will be dependent on the outcome of Periods 1 and 2, and may evaluate higher doses, the impact of a high-fat meal, and/or standard meal after dosing or BID dosing.
 

Time & Events	
 
Refer to Appendix 2: Schedule of Activities
 

Treatment Assignment	
 
This is an open-label, non-randomised study. A treatment allocation list will take the place of the randomisation schedule, which will be developed by the sponsor using RandAll NG.
 

Interim Analysis	
 
No formal interim analysis is planned for the study.
 
Analysed PK data will be reviewed after completion of Periods 1 to 3 of part A which will guide Periods 4, 5 and 6.
 
In Part C, there will be an interim review following completion of Periods 1 and 2 to determine the dose for Periods 3 and 4 (360 mg or 480 mg). Similarly, there will be an interim review following Periods 4 and 5 to determine dose, prandial state and and dosing regimen (QD or BID).
 
Data will be reviewed following completion of Part A to determine the formulation, doses, dosing frequency (QD or BID) and prandial state for Part B.
 

## 2.4. Statistical Hypotheses / Statistical Analyses

No formal hypothesis will be tested. However, point estimates and corresponding 90% confidence intervals will be derived for the ratio between each minitab MR formulation relative to the IR formulation for the geometric mean of Cmax, Cmin, C12, C24, peak-to-trough ratio, AUC(0-inf), AUC(0-12), and AUC(0-24). PK parameters at the 12 hour time point will only be included if BID dosing is used.

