4. OBJECTIVES AND ENDPOINTS

Objectives	Endpoints
Primary	

 To evaluate the single dose PK profile of GSK2982772 from each test minitab MR formulation in a capsule (120 mg) compared to the IR formulation (120 mg) 	
 GSK2982772 area under the curve from time zero to infinity ($AUC_{(0-inf)}$), area under the curve from time zero to the last measurable concentration ($AUC_{(0-t)}$), area under the curve from time zero to 24 hours ($AUC_{(0-24)}$), area under the curve from time zero to 12 hours ($AUC_{(0-12)}$), maximum observed concentration (C_{max}), Concentration at 12 hours post-dose (C_{12h}), Concentration at 24 hours post-dose (C_{24h}) and ratio of $C_{max} : C_{12h}$ and $C_{max} : C_{24h}$, relative bioavailability ($F_{rel\text{formulation}}$) based on AUC and C_{max}

 To evaluate the single dose PK profile of GSK2982772 from the MR tablet (240 mg) compared to the IR formulation (240 mg) 	
 GSK2982772 $AUC_{(0-inf)}$, $AUC_{(0-t)}$, $AUC_{(0-24)}$, $AUC_{(0-12)}$, C_{max}, C_{12h}, C_{24h} and ratio of $C_{max} : C_{12h}$ and $C_{max} : C_{24h}$, $F_{rel\text{formulation}}$ based on AUC and C_{max}
Secondary	

 To assess the impact of high fat meal on the PK of GSK2982772 following single dose administration of the selected minitab MR formulation in a capsule (120 mg) 	
 GSK2982772 $AUC_{(0-inf)}$, $AUC_{(0-t)}$, C_{max} and time to C_{max} (T_{max}), F_{relFE} based on AUC and C_{max}

 To determine if there are any dose dependant changes in the absorption of GSK2982772 following repeat dose 	
 GSK2982772 $AUC_{(0-24)}$, C_{max} and T_{max} if once daily (QD) dosing, on Day 1 and Day 3 GSK2982772 $AUC_{(0-12)}$, $AUC_{(12-24)}$, C_{max}

Objectives	Endpoints
administration of the selected minitab MR formulation in a capsule at target daily doses of 30, 60 and 240 mg	and T_{max} after morning dose, C_{max} and T_{max} after evening dose if twice daily (BID) dosing, on Day 1 and Day 3

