10. STATISTICAL CONSIDERATIONS

10.1. Hypotheses

No formal hypothesis will be tested. However, point estimates and corresponding 90% confidence intervals will be derived for C_{max} , $AUC_{(0-inf)}$, C_{12} and C_{24} and peak to trough concentration ratio for each test minitab MR formulation in a capsule (120 mg) relative to the IR formulation (120 mg).

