Descriptive statistics (n, arithmetic mean, standard deviation [SD], 95% CI, minimum, median and maximum,) will be calculated by treatment for all PK concentrations over time and for the derived PK parameters. In addition, for loge-transformed PK parameter variables geometric mean, 95% CI and $\%CV_b$ ($100 * \sqrt{(\exp(SD^2) - 1)}$) will be provided, where the SD is the standard deviation of log-transformed data.

Endpoint	Statistical Analysis Methods
Primary	
The primary PK endpoints to compare MR formulations with IR formulations will be summarised descriptively. Ratio of $AUC_{(0-inf)}$, $AUC_{(0-24)}$, ($AUC_{(0-t)}$, if $AUC_{(0-inf)}$ cannot be derived), C_{max}, C_{12} and C_{24} for MR formulation to IR formulation will be computed with 90% CI. C_{max} to C_{12h} and C_{max} to C_{24h} ratio for each MR formulation (120 mg or 240 mg) and the corresponding total dose of IR formulation (120 mg or 240 mg) will be computed with 90% CI.

Secondary	
The secondary endpoints for food effect will be summarised descriptively. In addition, log-transformed $AUC_{(0-inf)}$ ($AUC_{(0-t)}$, if $AUC_{(0-inf)}$ cannot be derived), C_{12h}, C_{24h}, and C_{max} will be analysed using a mixed effects model with regimen as a fixed effect and subject within sequence as a random effect. Point estimates and corresponding 90% CI will be computed for the differences for each GSK2982772 MR formulation (120 mg, 240 mg, 360 mg or 480 mg) taken in the fed state (test) vs the same dose in the fasted state (reference) using the residual error from the model (MSE). The point and interval estimates on the log-scale will then be exponentially back transformed to give estimates of the ratios of geometric means and 90% CI.
 
Within-subject coefficients of variation for $AUC_{(0-inf)}$ and C_{max} will be calculated based on the log_e-Normal distribution: $CV_w (\%) = \sqrt{\exp(mse) - 1} \times 100$, where MSE is the residual error from the model.
 
Statistical analysis of the PK endpoint T_{max} of each GSK2982772 MR formulation administered under both fed and fasted conditions will be separately analysed non-parametrically [Hauschke, 1990]. The point estimates for the medians for each treatment, the median difference and 90% CI for the median difference will be calculated for the contrast (test-reference).

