### 2.2. Study Objective(s) and Endpoint(s)

[figure not shown]
Objectives	Endpoints
Primary Objectives	Primary Endpoints

 
To evaluate the single dose PK profile of GSK2982772 from each test minitab Modified Release (MR) formulation in a capsule (120 mg) compared to the IR formulation (120 mg)
 
	
 
GSK2982772 area under the curve from time zero to infinity (AUC(0-inf)), area under the curve from time zero to the last measurable concentration AUC(0-t), area under the curve from time zero to 24 hours AUC(0-24), area under the curve from time zero to 12 hours AUC(0-12), maximum observed concentration (Cmax), Concentration at 12 hours post-dose (C12h), Concentration at 24 hours post-dose (C24h) and ratio of Cmax : C12h and Cmax : C24h, relative bioavailability (Frelformulation) based on AUC and Cmax
 

 
To evaluate the single dose PK profile of GSK2982772 from a (matrix monolithic) MR tablet (240mg) compared to the IR formulation (240mg).
 
	
 
GSK2982772 AUC(0-inf), AUC(0-t), AUC(0-24), AUC(0-12), Cmax, C12h, C24h, Cmax:C12h and Cmax:C24h, Frelformulation based on AUC and Cmax.
 

Secondary Objectives	Secondary Endpoints

 
To assess the impact of high fat meal on the PK of GSK2982772 following single dose
 
	
 
GSK2982772 AUC(0-inf), AUC(0-t), Cmax, time to Cmax (Tmax), FrelFE based on AUC and Cmax,
 

Objectives	Endpoints
administration of the selected minitab MR formulation in a capsule (120 mg)	

 
To determine if there are any dose dependant changes in the absorption of GSK2982772 following repeat dose administration of the selected minitab MR formulation in a capsule at target daily doses of 30, 60 and 240 mg
 
	
 
GSK2982772 AUC(0-24), Cmax, and Tmax if once daily (QD) dosing, on Day 1 and Day 3
 
GSK2982772 AUC(0-12), AUC(12-24), Cmax, and Tmax after morning dose, Cmax and Tmax after evening dose if twice daily (BID) dosing, on Day 1 and Day 3
 

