## 5. CONSIDERATIONS FOR DATA ANALYSES AND DATA HANDLING CONVENTIONS

### 5.1. Study Treatment & Sub-group Display Descriptors

Treatment Group Descriptions			
RandAll NG		Data Displays for Reporting	
Code	Description	Description	Order in TLF
Part A			
A	GSK2982772 120mg minitab MR RR1 oral single dose	MT-12h 120mg Fasted	2
B	GSK2982772 120mg minitab MR RR2 oral single dose	MT-8h 120mg Fasted	3
C	GSK2982772 120mg IR oral single dose	IR 120mg Fasted	1
D	GSK2982772 120mg minitab MR RR3 oral single dose	MT-12h 120mg Fed (Standard)	4
E	GSK2982772 120mg minitab MR RR4 oral single dose	n/a	5
F	GSK2982772 120mg minitab MR fed state	n/a	6
Part B			
G	GSK2982772 minitab MR Repeat Dose 1	MT-12h 120mg Fasted	1
H	GSK2982772 minitab MR Repeat Dose 2	MT-12h 240mg Fasted	2
J	GSK2982772 minitab MR Repeat Dose 3	MT-12h 300mg Fed (Standard)	3
Part C			
K	GSK2982772 240mg (matrix monolithic) MR oral single dose	MM-12h 240mg Fasted	2
L	GSK2982772 240mg IR oral single dose	IR 240mg Fasted	1
M	GSK2982772 360mg or 480mg (matrix monolithic) MR oral single dose	MM-12h 480mg Fasted	3
N*	GSK2982772 240mg (matrix monolithic) MR fed state	MM-12h 480mg Fed (Standard)	4
P	GSK2982772 360mg or 480mg (matrix monolithic) MR delayed fed (standard meal) or fed (high-fat meal)	MM-12h 480mg Delayed Fed (Standard)	5
Q	GSK2982772 dose tbd (matrix monolithic) MR QD or BID prandial state tbd.	MM-12h 240 mg Delayed Fed (High-Fat)	6

\* The randomization description for Period 4 of Part C (code N) indicates 240 mg, but the label has been updated to 480 mg to reflect the actual treatment administered.

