**NOTES:**

- Additional parameters may be included as required.
- No log transformation for  $T_{\max}$  nor any ratio (relative) endpoint.
- [1]:  $AUC_{(0-t)}$  if  $AUC_{(0-\infty)}$  cannot be derived
- [2]: If BID formulation.
- [3]: QD formulation only.

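### The SAP makes three protocol primary endpoints conditional on an undefined 'if BID' trigger in single-dose comparisons, and gives the planned peak-to-trough 90% CIs no model row; SAP 2.1 declares neither

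*SAP*

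**What the plan says.** Protocol section 4 names the primary endpoints for the 120 mg minitab and 240 mg tablet comparisons with IR. They include "area under the curve from time zero to 12 hours", the 12 h and 24 h concentrations, and both peak-to-trough ratios. SAP 2.2 repeats them for Part A as "Concentration at 12 hours post-dose (C12h), Concentration at 24 hours post-dose (C24h) and ratio of Cmax : C12h and Cmax : C24h" and lists the same parameters for Part C. Neither place mentions dosing frequency.

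For intervals, protocol 10.1 plans 90% CIs for Cmax, AUC(0-inf), C12, C24 and "peak to trough concentration ratio for each test minitab MR formulation in a capsule (120 mg) relative to the IR formulation". Protocol 10.4.1 adds AUC(0-24), and says the two peak-to-trough ratios for each MR formulation and "the corresponding total dose of IR formulation (120 mg or 240 mg) will be computed with 90% CI".

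SAP 2.4 promises a 90% CI for the MR/IR ratio of geometric means, including the peak-to-trough ratio and AUC(0-12), and then adds "PK parameters at the 12 hour time point will only be included if BID dosing is used". SAP 8.1.1.2 flags AUC(0-12), C12h and Cmax:C12h with note 2, if BID. SAP 8.1.5.1 lists AUC(0-12) and C12h in the primary model under the same condition. SAP 10.6.4.1 defines both for BID dosing. SAP 8.2.1.2 words its flag for the secondary analyses differently: "2]: If BID formulation". A note in 8.1.1.2 also rules out log transformation for Tmax and for ratio (relative) endpoints.

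SAP 2.1 reports no change from the protocol's planned analysis for the original protocol or amendment 1. For amendment 2 it reports only the added Part C analyses.

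**The concern.** A condition on twice-daily dosing makes little sense in a comparison where each participant takes one dose per period. Part A Periods 1 to 3 and Part C Periods 1 and 2 are all single-dose. SAP 5.1 describes the regimens in that way, for example "GSK2982772 120mg minitab MR RR1 oral single dose". The protocol uses BID conditions, but it attaches them to the secondary dose-dependence objectives and not to the primary endpoints.

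Read as it stands, the SAP could leave parameters that the protocol calls primary out of the final primary analysis, and could omit planned intervals, with no declared change. These parameters are not peripheral. A flatter concentration profile is a stated attraction of the MR formulation (protocol 3.1 and 5.4), and troughs and peak-to-trough ratios are what describe it.

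**Working it through.** No sample size, power or error-rate figure is involved. The check sets the sections side by side.

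| Parameter | Primary (protocol 4, SAP 2.2) | 90% CI planned (protocol 10.1, 10.4.1) | SAP 8.1.1.2 | SAP 8.1.5.1 model |
|---|---|---|---|---|
| AUC(0-inf) | yes | yes | yes | yes |
| AUC(0-t) | yes | fallback only | fallback | fallback |
| AUC(0-24) | yes | yes | yes | yes |
| AUC(0-12) | yes | no | if BID | if BID |
| Cmax | yes | yes | yes | yes |
| C12h | yes | yes | if BID | if BID |
| C24h | yes | yes | yes | yes |
| Cmax:C12h | yes | yes | if BID | no row |
| Cmax:C24h | yes | yes | yes | no row |

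**Counts.** Nine PK parameters are primary. Relative bioavailability, in the same cell, is left out because it is computed from AUC and Cmax. Three of the nine are gated. Seven have a planned 90% CI; the model treats 4 unconditionally, makes 1 conditional and omits 2 (4 + 1 + 2 = 7).

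**If the gate stays shut.** AUC(0-12) and Cmax:C12h are neither derived nor summarised. C12h keeps a descriptive summary, because SAP 8.1.2 summarises all concentrations over time, but loses its 90% CI. For AUC(0-12) the protocol owes only derivation and summary; its 90% CI is promised in SAP 2.4 alone.

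**Peak-to-trough, whatever the gate.** Neither ratio is in the 8.1.5.1 list. By title, Tables 3.4 and 3.17 cover AUC and C, and Tables 3.5 and 3.18 cover Tmax. SAP 8.1.2 supplies descriptive 95% CIs, not 90% CIs. If the no-log note covers these ratios, it contradicts the geometric-mean ratio in SAP 2.4.

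**Are the data there?** Protocol Table 2 schedules 12 h and 24 h samples for both MR and IR. Whether IR troughs can be quantified is a separate matter. Assume mono-exponential decline from dosing with the 2 to 3 h half-life in protocol 3.1; the assay limit is not given.

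- At 12 h: 12/3 = 4 to 12/2 = 6 half-lives. 2^-4 = 6.3% to 2^-6 = 1.6% remains, so an IR Cmax:C12h of about 16 to 64.
- At 24 h: 24/3 = 8 to 24/2 = 12 half-lives. 2^-8 = 0.39% to 2^-12 = 0.02% remains, so an IR Cmax:C24h of about 256 to 4096.

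On this assumption log(Cmax:C12h) is likely to be computable for IR, while log(Cmax:C24h) may not be.

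**The case against.** **The gate might open.** A reader might infer that nothing in the study can trigger the condition, so that the 12 h parameters are certain to drop out. The documents do not support that. The display labels in SAP 5.1 give formulation, dose and prandial state but no frequency, so the absence of BID from them proves nothing. SAP 2.4 does not tie BID to a period. SAP 2.3 and 8.2.5.2 keep BID open for Part B, and the treatment-code description for the last Part C regimen reads "GSK2982772 dose tbd (matrix monolithic) MR QD or BID prandial state tbd". A BID choice in either place could arguably satisfy the wording. Protocol 3.1 judged the slowest minitab suitable for QD, which makes a shut gate plausible but not certain. What remains is that a primary endpoint should not hang on an undefined trigger, or on a regimen chosen for another part or period.

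**The SAP leaves room to include them.** SAP 2.2 keeps the endpoints unconditional, and a note in 8.1.1.2 allows additional parameters as required. That makes the SAP inconsistent with itself; discretion to add a parameter is not a pre-specified analysis.

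**The peak-to-trough CI may need no model.** Protocol 10.4.1 can be read as asking for a 90% CI within each formulation. The SAP provides no 90% CI on that reading either, and protocol 10.1 asks for MR relative to IR, at least for the minitabs. With complete data, the MR/IR point estimate for Cmax:C24h is the Cmax ratio divided by the C24h ratio, so mainly the interval is missing. SAP 8.1.5.1 also limits its models to sufficient data, which could exclude Cmax:C24h. The no-log note may refer only to relative bioavailability. These points narrow this part of the finding but do not remove it.

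**Non-quantifiable troughs.** A reader might also infer that the SAP has no rule for them on the log scale. That cannot be asserted: SAP 10.5.2 sets values to zero for concentration summaries and refers to a guideline that is not among these documents.

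**Conclusion.** The concern holds as a conflict between the protocol and the SAP, and within the SAP. Three of nine primary PK parameters are unconditional in the protocol and gated on an undefined condition in the SAP. Two of seven planned 90% CIs have no row in the primary model. SAP 2.1 declares neither. That the two groups of sections disagree is certain from the text; actual loss of the 12 h outputs depends on how BID is read and on what was dosed.

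The consequence is limited to the completeness and pre-specification of final primary reporting. No hypothesis is tested, so no error rate is at stake. Nor should a reader infer that the QD or BID decision was made without these parameters: the interim package in protocol 5.1.1 includes AUC(0-12), C12h and both ratios with no such condition.

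**What to change.** - In the primary MR versus IR analyses (Part A Periods 1 to 3, Part C Periods 1 and 2), remove the BID condition for AUC(0-12), C12h and Cmax:C12h in SAP 2.4, 8.1.1.2, 8.1.5.1 and 10.6.4.1. If the restriction is intended, declare and justify it in SAP 2.1 and define what BID refers to.
- For AUC(0-12), restore derivation and summary. Modelling it with a 90% CI is optional, since the protocol does not ask for that.
- Add log(Cmax:C12h) to SAP 8.1.5.1 and to Tables 3.4 and 3.17. Add log(Cmax:C24h) where 24 h IR concentrations are quantifiable; otherwise report it descriptively and say so.
- State that the no-log note in SAP 8.1.1.2 does not cover these two ratios.

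The cost is SAP wording, some extra table rows and up to four modelled endpoints: AUC(0-12), C12h and the two log ratios. No new samples are needed.

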### **3. PLANNED ANALYSES**

#### **3.1. Interim Analyses**

No formal statistical analyses are planned.

##### **Part A**

After Periods 1 to 3 are complete, the PK and safety data will be analysed which will guide Periods 4, 5 and 6. Periods 4, 5 and 6 will be flexible and the dosing regimen will be dependent on the outcome of preceding periods. There will be the option to either optimise the MR release duration and/or to evaluate the impact of food on the selected MR minitablet formulation in a capsule. There will also be the option to cancel Periods 5 and 6 if an optimal formulation is determined in Periods 1 or 2.

There will be an interim data review following final period of Part A to determine the formulation, doses, dosing frequency (QD or BID) and prandial state for Part B. The data, consisting of summary report of PK and safety endpoints will be sent to the sponsor by Quotient, from which the decision on formulation and prandial state selection or stopping the study will be made by the Quotient study team (i.e., PI, scientific lead and pharmacokineticist) and sponsor study team (as a minimum the sponsor's medical monitor, CPMS and GCSP). The decision will be documented and signed by the PI as per Quotient Clinical current SOP. Evidence of the decision will be retained in the ISF and GSK Trial Master File.

##### **Part B**

There will be no interim analysis during Part B of the study.

##### **Part C**

In Part C, there will be an interim review following completion of Periods 1 and 2 to determine the dose for Periods 3 and 4 (360 mg or 480 mg). Similarly, there will be an interim review following Periods 4 and 5 to determine dose, prandial state and dosing regimen (QD or BID). The data, consisting of summary report of PK and safety endpoints will be sent to the sponsor by Quotient, from which the decision on formulation and prandial state selection or stopping the study will be made by the Quotient study team (i.e., PI, scientific lead and pharmacokineticist) and sponsor study team (as a minimum the sponsor's medical monitor, CPMS and GCSP). The decision will be documented and signed by the PI as per Quotient Clinical current SOP. Evidence of the decision will be retained in the ISF and GSK Trial Master File.

#### **3.2. Final Analyses**

The final planned primary analyses will be performed after the completion of the following sequential steps:

1. All participants have completed the study as defined in the protocol.
2. All required database cleaning activities have been completed and final database release (DBR) and database freeze (DBF) has been declared by Data Management.

## 4. ANALYSIS POPULATIONS

Population	Definition / Criteria	Analyses Evaluated
All Subjects	
 
• All participants who were screened for eligibility and allocated a subject number.
 
	
 
• Selected Study Population
 

Safety	
 
• All participants who receive at least 1 dose of study treatment and will be the population for reporting of safety and study population data. Participants will be analyzed according to the treatment they actually received.
 
	
 
• Safety and Study Population
 

PK	
 
• Participants in the 'Safety Population' for whom a PK sample was obtained and analysed will be the population for reporting of PK data.
 
	
 
• PK
 

Refer to [Appendix 11](#): List of Data Displays which details the population used for each display.

